In- / Exclusion criteria	Х						
Biomarkers (blood sample)		Х	Х	Х	Х	Х	
Tumor tissue ⁹	Х				Х		
HR-QoL	Х			Х		Х	
Treatment (V1/V2)		Pembrolizumab 200 mg i.v	Pembrolizumab 200 mg i.v				

0316-ASG / NEOMUN

Study Phase Procedure	Screening	Treatment phase		Pre- Surgery	Dis-charge	End of treatment	Follow-up
Visit	SCR	V1	V2	PS	D	EOT	FU1 – FUx
Time windows	Day - 28 to 0	Day 1	Day 21 +/- 3 days	Day 43-50	Day 60-74	6 wks. after surgery	every 3 months
Concomitant medication	Х		Continuously				
Concomitant procedures	Х		Continuously				
Adverse events	Х	Continuously			X ⁷		
Subsequent cancer therapy							Х
Survival status							Х

¹ if clinically indicated. Consult a specialist if clinically abnormal and exclude any immune-related myocarditis.

² Full examination is required at baseline and end of treatment. Focused clinical examination shall prevail throughout the course of treatment.

³ Body height will only be measured at screening.

⁴ Full blood count including blood differential test will be performed at baseline, after start of treatment (V2) and further indicated time points throughout treatment and at end of study.

⁵ Sodium, potassium, calcium, magnesium, phosphate, AST, ALT, PTT/INR, LDH, total bilirubin, creatinine, creatinine clearance, albumin, tumor marker CEA, Cyfra 21-1

⁶ To be done at baseline and 3 weeks after start of treatment (V2) and further indicated time points throughout treatment and at end of study. If rising TSH is detected, a full assessment of fT3 and fT4 shall be performed and signs of hormone depletion shall be monitored clinically.

⁷ Follow-up of ongoing SAEs until resolution or stabilization. Serious adverse events are recorded until 90 days after last dose of IMP or for 6 weeks after surgery if the subject initiated new anticancer therapy (e.g. radiochemotherapy). Pregnancies occurring in a study subject are recorded from time of signed informed consent until 120 days after last dose of IMP.

⁸ Repeat assessment if SCR assessment is older than 7 days.

⁹ Post-op. tumor regression grading.

Safety reporting contact information (SAE / Pregnancy)

In the case of a serious adverse event (SAE) or pregnancy safety desk must be contacted within 24 hours.

Contact details for safety reporting are provided in the Investigator Site File.

The safety desk will inform MSD Germany Pharmacovigilance (Email:

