2.5 Secondary endpoints

- disease free survival
- overall survival

2.6 Exploratory endpoints:

- prognostic value of tumor shrinkage
- prognostic value of inflammatory infiltrates in and around the resected tumor
- serum- and tumor tissue cytokine concentrations
- multi-OMICS tissue analysis approach for markers and mechanisms

3 Overview of Study Design and Dosing Regimen

The study is designed as an open-label, single arm, prospective, monocentric, phase II study of pembrolizumab in a neoadjuvant setting in patients with non-small cell lung cancer of Stage II/IIIA suitable for surgery.

During the treatment phase, patients will receive intravenous pembrolizumab 200 mg q3wks. for 2 cycles or occurrence of non-tolerable toxicity. After completion of immunotherapy lobectomy or bilobectomy with curative intent is scheduled. After end of protocol treatment, patients will be treated individually according to local standards.

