5.2 Study Procedures

5.2.1 Screening Procedures (day -28 to 0)

NOTE: Any routine procedure which is performed during the screening window may be used as a screening assessment in this trial. Documentation of any screening procedure in the eCRF can only be performed after informed consent of the patient. All patients will be screened and screening procedures performed within 28 days prior to start of study treatment include the following:

Signed Informed ConsentObtained prior to any study specific assessment

AIO-Studien-gGmbH

Demographics and medical	○ Age, gender, race
history	 Tumor diagnosis
	 Previous and concurrent relevant diseases
	 Previous treatments
	 Tobacco consumption in pack years
Tumor measurement	See section 5.1.1
according to RECIST 1.1	
(CT or MRI)	
Tumor assessments	Whole body PET-CT and MRI brain scans (or CT
CT or MRI	brain if MRI is not feasible) are required.
Cardiac evaluation	12-lead ECG
Physical examination and	 Physical examination
vital signs	 Body height, weight
	 Vital signs measurements will include body
	temperature, pulse and blood pressure
ECOG performance status	See Appendix 1 – ECOG Performance Status
Serum pregnancy test	A serum pregnancy test will be performed in pre-
	menopausal women and women who are
	menopausal for < 2 years. In case the sampling
	date for serum pregnancy testing exceeds 7 days
	before treatment start, a urine test is required for
	confirmation of the absence of pregnancy.
Lung function	Body plethysmography / blood gas analysis,
	diffusion capacity
Hematology	Hemoglobin, erythrocytes, platelets, leukocytes,
	absolute neutrophils (ANC), basophils, eosinophils,
	lymphocytes, monocytes
Clinical chemistry	Sodium, potassium, calcium, magnesium, albumin
	phosphate, AST, ALT, PTT/INR, LDH, total
	bilirubin, creatinine, creatinine clearance (see
	section 18.4 Appendix 4), TSH
tumor marker	CEA, Cyfra 21-1

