5.2.2 Treatment Phase

For V1 no particular assessments are required. However, the following assessments need to be repeated if the Screening assessment is older than 7 days measured from first dose of IMP: Hematology, pregnancy test, clinical chemistry, coagulation, vital signs. ConMed and AE documentation may need to be updated if required.

During treatment phase the following assessments and procedures will be performed for V2 unless a different time point is mentioned specifically:

Cardiac evaluation	12-lead ECG, transthoracic echocardiogram (TTE)
	if clinically indicated
Physical examinations and	Physical examination
vital signs	Body weight, BSA
	Vital signs measurements will include body
	temperature, pulse and blood pressure
ECOG performance status	Day 1 of each immunotherapy cycle, see

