6.3 Dose Modifications

6.3.1 Dose Modification and Discontinuation of pembrolizumab for adverse reactions Dose modifications in terms of dose reductions are not allowed in this study. Dose modifications in terms of pausing of treatment or discontinuation may be required due to AEs.

Adverse events (both non-serious and serious) associated with pembrolizumab exposure may represent an immunologic etiology. These adverse events may occur shortly after the first dose or several months after the last dose of treatment. Pembrolizumab must be withheld for drug-related toxicities and severe or life-threatening AEs as per Table 1 below. See Section 6.3.2 for supportive care guidelines, including use of corticosteroids.

Toxicity	Hold Treatment For Grade	Timing for Restarting Treatment	Discontinue Treatment Discontinuation
Diarrhea/Colitis	2-3	Toxicity resolves to Grade 0-1	Toxicity does not resolve within 12 weeks of last dose or inability to reduce corticosteroid to 10 mg or less of prednisone or equivalent per day within 12 weeks
	4	Permanently discontinue	Permanently discontinue
AST, ALT, or 2 Increased Bilirubin 3-4	2	Toxicity resolves to Grade 0-1	Toxicity does not resolve within 12 weeks of last dose
	3-4	Permanently discontinue (see exception below) ^a	Permanently discontinue
Type 1 diabetes mellitus (if new onset) or Hyperglycemia	T1DM or 3-4		Resume pembrolizumab when patients are clinically and metabolically stable

Table 1: Dose Modification Guidelines for Drug-Related Adverse Events: For more details please see
 6.3.2 'supportive measure guidelines'.

AIO-Studien-gGmbH

Toxicity	Hold Treatment For Grade	Timing for Restarting Treatment	Discontinue Treatment Discontinuation
Hypophysitis	2-4	Toxicity resolves to Grade 0-1. Therapy with pembrolizumab can be continued while endocrine replacement therapy is instituted	Toxicity does not resolve within 12 weeks of last dose or inability to reduce corticosteroid to 10 mg or less of prednisone or equivalent per day within 12 weeks
Hyperthyroidism	3	Toxicity resolves to Grade 0-1	Toxicity does not resolve within 12 weeks of last dose or inability to reduce corticosteroid to 10 mg or less of prednisone or equivalent per day within 12 weeks
	4	Permanently discontinue	Permanently discontinue
Hypothyroidism	2-4	Therapy with pembrolizumab can be continued while thyroid replacement therapy is instituted	Therapy with pembrolizumab can be continued while thyroid replacement therapy is instituted

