- When symptoms improve to Grade 1 or less, steroid taper should be started and continued over no less than 4 weeks.
- Type 1 diabetes mellitus (if new onset, including diabetic ketoacidosis [DKA]) or ≥ Grade 3 Hyperglycemia, if associated with ketosis (ketonuria) or metabolic acidosis (DKA)
 - For **T1DM** or **Grade 3-4** Hyperglycemia
 - Insulin replacement therapy is recommended for Type I diabetes mellitus and for Grade 3-4 hyperglycemia associated with metabolic acidosis or ketonuria.
 - Evaluate patients with serum glucose and a metabolic panel, urine ketones, glycosylated hemoglobin, and C-peptide.
- Hypophysitis:
 - For Grade 2 events, treat with corticosteroids. When symptoms improve to Grade 1 or less, steroid taper should be started and continued over no less than 4 weeks. Replacement of appropriate hormones may be required as the steroid dose is tapered.
 - For Grade 3-4 events, treat with an initial dose of IV corticosteroids followed by oral corticosteroids. When symptoms improve to Grade 1 or less, steroid taper should be started and continued over no less than 4 weeks. Replacement of appropriate hormones may be required as the steroid dose is tapered.

• Hyperthyroidism or Hypothyroidism:

Thyroid disorders can occur at any time during treatment. Monitor patients for changes in thyroid function (at the start of treatment, periodically during treatment, and as indicated based on clinical evaluation) and for clinical signs and symptoms of thyroid disorders.

- Grade 2 hyperthyroidism events (and Grade 2-4 hypothyroidism):
 - In hyperthyroidism, non-selective beta-blockers (e.g. propranolol) are suggested as initial therapy.
 - In hypothyroidism, thyroid hormone replacement therapy, with levothyroxine or liothyronine, is indicated per standard of care.
- **Grade 3-4** hyperthyroidism
 - Treat with an initial dose of IV corticosteroid followed by oral corticosteroids. When symptoms improve to Grade 1 or less, steroid taper should be started and continued over no less than 4 weeks. Replacement of appropriate hormones may be required as the steroid dose is tapered.
- Hepatic:
 - For Grade 2 events, monitor liver function tests more frequently until returned to baseline values (consider weekly).
 - Treat with IV or oral corticosteroids
 - For Grade 3-4 events, treat with intravenous corticosteroids for 24 to 48 hours.
 - When symptoms improve to Grade 1 or less, a steroid taper should be started and continued over no less than 4 weeks.

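### The hold for new-onset type 1 diabetes or Grade 3-4 hyperglycemia has no scheduled glucose test behind it, so dose 2 can be given with no glucose result

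*Protocol*

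**What the plan says.** **The hold.** Section 6.3.1 makes the withholding rules of Table 1 mandatory. One row reads "Type 1 diabetes mellitus (if new onset) or Hyperglycemia", with the hold applying to type 1 diabetes or Grade 3-4. The condition for restarting is "Resume pembrolizumab when patients are clinically and metabolically stable".

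**The regimen.** Under Section 3, "patients will receive intravenous pembrolizumab 200 mg q3wks. for 2 cycles or occurrence of non-tolerable toxicity".

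**The scheduled chemistry.** Footnote 5 of the Schedule of Study Assessments defines the panel as "Sodium, potassium, calcium, magnesium, phosphate, AST, ALT, PTT/INR, LDH, total bilirubin, creatinine, creatinine clearance, albumin, tumor marker CEA, Cyfra 21-1". SAP 1.5 repeats it unchanged. The screening list in Section 5.2.1 begins "Sodium, potassium, calcium, magnesium, albumin" and continues with the same kind of analytes. At V1 nothing new is drawn: "the following assessments need to be repeated if the Screening assessment is older than 7 days measured from first dose of IMP", which repeats the same panel.

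**The one mention of a glucose measurement.** Section 6.3.2, under type 1 diabetes or Grade 3-4 hyperglycemia, says: "Evaluate patients with serum glucose and a metabolic panel, urine ketones, glycosylated hemoglobin, and C-peptide". The heading of that entry qualifies the hyperglycemia part with "if associated with ketosis (ketonuria) or metabolic acidosis (DKA".

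**The concern.** A hold rule needs an input. For hyperglycemia that input is a glucose value, and the protocol does not schedule one. The glucose work-up in Section 6.3.2 starts after someone has already identified diabetes or severe hyperglycemia, so it characterises an event and does not find one.

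What is at stake is a patient safety decision. A patient who develops hyperglycemia after dose 1 without clear symptoms could receive dose 2 at V2, although Table 1 says treatment must be held. The site would have followed every scheduled step.

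There is also a smaller gap at baseline. If diabetes was undiagnosed before entry, no screening glucose exists against which to judge whether a later finding is new.

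**Working it through.** The plan gives no figure on this point, so there is none to reproduce. The check compares the rule with every list that could supply its input, followed by simple counts.

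**1. Decisions that a hold can change.** There are 2 doses per patient, and the row covers drug-related events, which can arise only after dose 1. Decisions per patient: 2 − 1 = 1, namely dose 2 at V2 (Day 21 ± 3). With N = 30, the ceiling is 1 × 30 = 30 decisions. Patients who stop after dose 1, or who have already passed V2 when an amendment takes effect, reduce this number.

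**2. Where glucose could be required.**

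| Source | Glucose listed? |
|---|---|
| Eligibility laboratory criteria (4.2, item 11) | No |
| Schedule of Study Assessments, footnote 5 | No |
| Screening chemistry (5.2.1) | No |
| V1 repeat (5.2.2) | No, same panel repeated |
| V2 chemistry and coagulation (5.2.2) | No |
| Pre-surgical, discharge and EOT lists (5.2.3 to 5.2.5) | No |
| General laboratory section (5.1.4) | No analyte added |
| Blood gas parameters (5.1.2.6) | No; pH is listed |
| SAP 1.5 and SAP 6.3.1, including the unit tables | No |

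The chemistry panel is scheduled at 5 visits (SCR, V2, PS, D, EOT), and glucose is on 0 of the 5. Required glucose results before dose 2: 0.

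**3. What could still reveal the event before dose 2.** Blood gas with pH is scheduled at 4 visits (SCR, V2, PS, EOT), so V2 is covered. A low pH would point to the acidotic form but does not measure glucose. V2 also has a physical examination, body weight and electrolytes, and adverse events are collected continuously. PET-CT falls at screening and pre-surgery, and the protocol asks for no glucose with it. Surgery follows both doses. Neither supplies an on-treatment value in time for V2.

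**4. Comparison with other rows of Table 1.** AST, ALT and bilirubin are scheduled for the hepatic row, creatinine for the renal row and TSH for the thyroid rows. The diabetes and hyperglycemia row has no matching scheduled test, and neither document gives a reason.

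**5. Tests needed to close the gap.** Screening and V2: 2 × 30 = 60. If every patient also needs the V1 repeat: 60 + 30 = 90. Keeping glucose on PS, D and EOT as well would add 3 × 30 = 90, but all of these come after the last dose.

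**The case against.** The strongest reply is that the protocol works from recognised events. Table 1 is a guideline for drug-related adverse events, not a screening programme. It also holds treatment for Grade 2-4 hypophysitis, yet schedules no pituitary or adrenal hormone apart from TSH. Symptoms, examination and the V2 blood gas can all bring diabetes to light. Section 6.3.2 ties its hyperglycemia entry to ketosis or acidosis, and pH bears on the acidotic form. Nothing stops the site from measuring glucose as local routine.

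Much of this stands. A reader might infer that the row cannot be applied at all. The documents do not support that: the row works once an event comes to notice. What remains is the patient whose hyperglycemia has not yet produced symptoms or acidosis. Table 1 itself carries no ketosis or acidosis qualifier, so such a patient falls under the hold if the grade is met.

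A reader might also infer that there is no baseline of any kind. That goes too far. Screening records medical history and previous treatments, and concomitant medication is recorded from 28 days before dose 1, so known diabetes is captured. Once an event is suspected, Section 6.3.2 adds glycosylated hemoglobin and C-peptide. Only previously undiagnosed diabetes lacks a screening value for comparison.

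A similar criticism of the thyroid reflex in footnote 6, which names only a rising TSH, does not hold up. TSH is measured at five visits, Section 6.3.2 provides for thyroid monitoring as clinically indicated, and Section 7.6.5 requires unexplained abnormal values to be repeated and followed.

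**Conclusion.** The point holds as a minor design gap. A fully compliant site can give dose 2 without a glucose value, although a mandatory hold rule depends on one. It concerns one decision per patient and at most 30 in the trial.

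Few patients are expected to be affected, but the documents do not allow a numerical bound. It is tempting to take the rate of the fifth-ranked drug-related serious event in Section 1.2.4 as a ceiling, since diabetes is not among the five. That does not work:

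- The rate caps a single reported term, and diabetes-type events may be spread over several terms.
- It covers whole treatment courses, not the roughly three weeks after one dose.
- It says nothing about silent or non-serious Grade 3-4 hyperglycemia, which is where a scheduled test would add most.

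A reader might also infer a material distortion of the Grade 2-4 adverse event endpoint. The documents give no incidence from which to show one, and none is claimed.

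The conclusion assumes only that the laboratory lists are complete as written. If the site already measures glucose at every visit, the practical risk is smaller, but the value is still neither required by the protocol nor summarised under the SAP.

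**What to change.** - **Protocol.** Add glucose to the clinical chemistry panel in footnote 5 and in Sections 5.2.1 and 5.2.2, at screening and at V2. The existing V1 repeat for results older than 7 days then covers it.
- **Timing.** State in Section 5.2.2 that the V2 glucose result is reviewed before dose 2 is infused. Without this sentence the sample could be taken and the infusion given before the result is read.
- **SAP.** Add glucose to the schedule copy in SAP 1.5, and to the data points and unit table in SAP 6.3.1.
- **Optional.** Keep glucose on the PS, D and EOT panels. This helps adverse event detection only, since no dosing decision remains.

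Table 1 and Section 6.3.2 can stay as they are.

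**Cost.** A small protocol amendment under Section 12, one eCRF field with its reference range, and about 60 to 90 glucose results on blood already drawn and analysed at the local laboratory. Some mild values that call for no action will have to be reviewed.

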1.1 Disease Background

In Germany lung cancer is the most frequent form of cancer death in male and the third most frequent malignant disease in women [5]. A steady trend to increasing incidence numbers in the female population is observed and the most important risk factor for disease remains tobacco smoking. Lung cancer diagnosis is associated with a poor prognosis and 5-year survival rates are 16% in male and 21% in female patients [5]. Non-small cell lung cancer (NSCLC) is the dominant form comprising 85-90% of all lung cancers. NSCLCs are divided into three main subgroups; squamous cell carcinoma, large cell carcinoma and adenocarcinomas, the latter of which is generally the most frequent (60-70% of NSCLC). Curative intent surgery represents the primary treatment modality in approximately 30% of NSCLC patients. However, even in patient cohorts of specialized high volume lung cancer centers more than 50% of patients develop tumor recurrence within 5 years following curative intend surgery. (see Figure 1).

1.2 Pembrolizumab

1.2.1 Pembrolizumab Background

Pembrolizumab is a potent and highly selective humanized monoclonal antibody (mAb) of the IgG4/kappa isotype designed to directly block the interaction between PD-1 and its ligands, PD-L1 and PD-L2. KEYTRUDA[®] (pembrolizumab) has recently been approved in the United Stated and the E.U. for the treatment of patients with unresectable or metastatic melanoma and disease progression following ipilimumab and, if BRAF V600 mutation positive, a BRAF inhibitor. Additionally, pembrolizumab has received marketing approval for the treatment of locally advanced or metastatic non-small cell lung carcinoma (NSCLC) in adults whose tumors express PD-L1 and who have received at least one prior chemotherapy regimen.

On 05-Aug-2016 the US FDA approved KEYTRUDA[®], at a fixed dose of 200 mg Q3W, for the treatment of patients with recurrent or metastatic head and neck squamous cell carcinoma (HNSCC) with disease progression on or after platinum-containing

chemotherapy. Under the FDA's accelerated approval regulations, this indication for KEYTRUDA[®] is approved based on tumor response rate and durability of response. For HNSCC patients, PD-L1 testing is not needed prior to use of KEYTRUDA[®]. The FDA-approved dose of KEYTRUDA[®] is 200 mg Q3W.

1.2.2 Mechanism of Action

The PD-L1 and PD-L2 can be found on tumor cells and this receptor-ligand interaction is one of the major pathways used by the cancerous cells to suppress the body's immune response to the tumor, as binding of either PD-L1 or PD-L2 to PD-1 inhibits T cell activation triggered through the T cell receptor.

Evidence shows a correlation between tumor-infiltrating lymphocytes in cancer tissue and a favorable prognosis in various malignancies. Correspondingly, a high expression of PD-L1 (and to a lesser extent PD-L2) on tumor cells has been found to correlate with a poor prognosis and survival rate in various types of cancer. Pembrolizumab can prevent the binding of PD-L1 and PD-L2 to the PD-1 receptor thus preventing its tumor suppressing effects on the immune response. Therefore, it is predicted that Pembrolizumab has the potential to improve the prognosis and survival rates of patients with various malignancies. For this reason Pembrolizumab is being developed to treat patients with various malignancies.

1.2.3 Pembrolizumab Non Clinical Data

1.1.1.1 Pharmacology

Pembrolizumab binds to human and Cynomolgus monkey PD-1 with comparable affinity and blocks the binding of human and Cynomolgus monkey PD-1 to PD-L1 and PD-L2 with comparable potency. Pembrolizumab does not cross-react with dog, rat, or mouse PD-1. Pembrolizumab does not bind immunoglobulin (Ig) superfamily members cluster of differentiation 28 (CD28), cytotoxic T-lymphocyte-associated protein 4 (CTLA-4), or inducible T-cell costimulator (ICOS).

Pembrolizumab strongly enhances T-lymphocyte immune responses in cultured blood cells from healthy human donors, cancer subjects, and nonhuman primates. In T-cell activation assays using human donor blood cells, the half-maximal effective concentration has been approximately 0.1 to 0.3 nanomolar (nM). In addition to

interleukin-2 (IL-2), tumor necrosis factor alpha (TNF α), interferon gamma (IFN χ), and levels of other cytokines were found to be modulated by pembrolizumab. The antibody potentiates existing immune responses only in the presence of antigen and does not nonspecifically activate T-cells. In the in vitro peripheral blood mononuclear cell (PBMC) and whole blood cytokine release assays, the cytokine levels induced by pembrolizumab were low and comparable to those induced by trastuzumab. Pembrolizumab does not induce antibody-dependent cell-mediated cytotoxicity (ADCC) or complement-dependent cytotoxicity (CDC). Using anti-murine PD-1 surrogate antibodies, PD-1 blockade has been shown to significantly inhibit tumor growth in a variety of syngeneic murine tumor models. In these experiments in mice, anti-PD-1 therapy is synergistic with chemotherapeutic agents such as gemcitabine and 5-fluorouracil (5-FU), and combination therapy results in increased complete tumor regression rates in vivo. Studies also revealed that immunosuppressive doses of dexamethasone included in combination with agents used in standard-of-care treatment for NSCLC do not reduce the anti-tumor efficacy of an anti-murine PD-1 surrogate antibody.

